**Table 3 Pre-Specified Abnormal Laboratory Criteria**

Term	Criteria
AST (U/L) or ALT (U/L) and Total bilirubin (mg/dL)	Meet all of the following criteria: AST $>3 \times$ ULN or ALT $>3 \times$ ULN Total bilirubin value $>2 \times$ ULN at same timepoint

ALT=alanine aminotransferase; AST=aspartate aminotransferase; ULN=upper limit of normal.

#### **4.2.1.4 Vital Signs**

For each of the vital signs (diastolic blood pressures, systolic blood pressures, respiratory rate and pulse rate), summary statistics of observation and the change from baseline will be presented for each scheduled time point.

Baseline is defined as the last assessment prior to treatment.

#### **4.2.1.5 Body Temperature**

Body temperature is collected in the patient diary 4 times daily for Day 1–3, twice daily for Day 4–9 and once daily thereafter. Summary statistics of observation and the change from baseline in body temperature will be presented for each recorded time point.

Baseline is defined as the first recorded assessment on Day 1 after treatment. Patients who do not have body temperature recorded on Day 1 after the start of treatment will have their baseline body temperature set to missing.

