4.5.4 Vital Signs

Vital signs will include measurements of respiratory rate, pulse rate, and systolic and diastolic blood pressure as well as tympanic temperature.

Temperature will also be measured and recorded by parents/caregivers in patients eDiary (Section 4.5.6).

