6.5 SAFETY ANALYSES

The safety evaluable population will be used for all analyses.

All verbatim adverse event terms will be mapped to MedDRA thesaurus terms, and adverse event severity will be graded according to NCI CTCAE v5.0.

The safety of baloxavir marboxil will be evaluated from adverse events, vital sign measurements (*including parent/caregiver recorded temperature*) and clinical laboratory tests. Safety parameters will be summarized or listed for the safety population.

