^a Pre-screening assessment is not required if the patient has a negative COVID-19 test result and positive influenza test performed as SOC within 48 hours of screening recorded in their medical records

^b OpV1 and OpV2 are optional visits to be performed at the discretion of the investigator or parent/caregiver, for example, in the event of persistent influenza symptoms.

^c Test is not required if the patient has a positive influenza test result performed as SOC within 48 hours of screening recorded in their medical records

^d Test is not required if the patient has negative COVID-19 test results performed as SOC within 48 hours of screening recorded in their medical records.

^e Prior therapies will also be reviewed.

^f The parent/caregiver will assess and record in the patient diary, body temperature (tympanic assessment) four times daily (morning, noon, evening, and bedtime) on Days 1 to 3; twice daily (morning and evening) on Days 4 to 9; once daily on Days 10 to 15. The first temperature recorded by the parent/caregiver will be measured post-dose.

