**Table 4 CARIFS Questionnaire Data Recording Time Periods**

Period	Time a
Morning	05.00–10.59
Noon	11.00–14.59
Evening	15.00–18.59
Bedtime	19.00–23.59

a data should not be recorded between 00.00 and 04.59.

In the case where the device was activated after Day 1, the actual day will be used as the assessment day rather than the device-labelled day. In the case where assessments should be recorded twice daily (morning and evening) but are recorded for more than two time periods, only the morning and evening assessments will be presented in summaries over time. In the case where assessments should be recorded once daily but are recorded for more than one time period, a conservative approach will be taken to select the data points to be included in the summaries over time.

In the case where the recorded time of an assessment is outside the period time window for that assessment, the end time of the period should be imputed as the assessment time.

In the case where the assessment time falls into the period between 00.00 and 04.59 (due to technical error) the assessment date will be imputed to the date prior to recorded assessment date and the assessment time will be imputed to the end time of the period time window.

The possible scores for the 18 symptoms specified in the CARIFS questionnaire (see [Appendix 4](#)) are:

- 0 (“No Problem”)
- 1 (“Minor Problem”)
- 2 (“Moderate Problem”)
- 3 (“Major Problem”)
- 4 (“Don’t Know/Not Applicable”)

The imputation method used in the derivation of time to alleviation of influenza signs and symptoms is described below. No further imputation methods will be used.

In all time to event analyses, patients who withdraw prior to event of interest will be censored at the last observation timepoint.

If the number of patients in the ITTi set is small, then listings may be provided.

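### SAP 4.2.1.4 leaves clinic tympanic temperature out of the vital signs it summarises, so no specified summary shows temperature change from before treatment

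*SAP*

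**What the plan says.** Protocol 4.5.4 lists the clinic vital signs as respiratory rate, pulse rate, "systolic and diastolic blood pressure as well as tympanic temperature". It then adds the caregiver's diary temperature as a further measurement. The schedule (Protocol Appendix 1, repeated in SAP Appendix 2) marks vital signs at V1 Screening, not at V1 Post-dose. It marks them again at Visits 2 to 5 (Days 2, 4, 6 and 10), and conditionally at the optional visits and Day 29.

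Vital signs are part of the primary safety endpoint (Table 1 in both documents). Protocol 6.5 bases the safety evaluation on adverse events, "vital sign measurements (*including parent/caregiver recorded temperature*) and clinical laboratory tests".

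SAP 4.2.1.4 names four vital signs: diastolic and systolic blood pressure, respiratory rate and pulse rate. For these, "Baseline is defined as the last assessment prior to treatment". SAP 4.2.1.5 covers temperature separately and from the diary alone: "Body temperature is collected in the patient diary 4 times daily for Day 1–3", and less often after that. It summarises observed values and change, and "Baseline is defined as the first recorded assessment on Day 1 after treatment". Infants with no Day 1 post-dose entry "will have their baseline body temperature set to missing". Footnote f of the schedule confirms the timing: "The first temperature recorded by the parent/caregiver will be measured post-dose".

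**The concern.** The protocol collects a pre-dose temperature on the same occasion as the other vital signs, but the SAP gives it no summary. The temperature change that is summarised starts after dosing. A reader of the safety tables would take change from baseline to mean change from before treatment. That is what it means for the other vital signs, but not for temperature.

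Two things are at stake. First, any rise or fall between dosing and the first home reading is missing from the change column of a primary safety parameter. Second, an infant with no Day 1 diary entry has no temperature change at all, although a pre-dose clinic value should exist. With about 30 infants and cohort minimums of 8, 4 and 3, avoidable gaps are noticeable.

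**Working it through.** The plan states no figure to reproduce here. The check is a comparison of the texts, followed by an identity that shows what the change column contains.

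**1. Baselines across the SAP, set against what is scheduled on Day 1**

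| Data | Pre-dose value scheduled? | SAP baseline |
|---|---|---|
| Blood pressure, respiratory rate, pulse (4.2.1.4) | Yes, V1 Screening | Last pre-dose |
| Clinic tympanic temperature | Yes, V1 Screening | None; no summary specified |
| Diary temperature (4.2.1.5) | No, first reading is post-dose | First Day 1 post-dose |
| CARIFS (4.3.1) | No, first assessment is post-dose | First Day 1 post-dose |
| Laboratory tests (4.2.1.3) | No, post-dose only on Day 1 | Day 1 post-dose |
| Virology (4.3.2) | Yes, V1 Screening | Last pre-dose, else first Day 1 post-dose |

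Wherever a pre-dose value is scheduled, the SAP uses it, except for clinic temperature. The gap therefore lies in the list in 4.2.1.4. The post-dose diary baseline follows from the diary schedule.

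**2. What the change column contains**

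Let T0 be the pre-dose clinic temperature, T1 the first post-dose diary reading and Tk a later reading. Leaving aside differences between observers and devices:

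reported change = Tk - T1 = (Tk - T0) - (T1 - T0)

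The early change, T1 - T0, is removed from every reported value.

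**3. Illustration (assumed temperatures)**

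Take T0 = 38.5 °C and Tk = 36.8 °C, so the change from pre-dose is 36.8 - 38.5 = -1.7 °C.
- Early fall 0.3 °C: 36.8 - 38.2 = -1.4 °C reported.
- Early fall 0.5 °C: 36.8 - 38.0 = -1.2 °C reported.
- Early fall 1.0 °C: 36.8 - 37.5 = -0.7 °C reported.

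An early rise can reverse the sign. With T0 = 38.0, T1 = 39.0 and Tk = 38.5 °C, the reported change is 38.5 - 39.0 = -0.5 °C. The change from pre-dose is 38.5 - 38.0 = +0.5 °C.

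**4. Missing baselines (assumed rates)**

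If 5%, 10% or 20% of 30 infants had no Day 1 post-dose entry, the expected number without a change value is 30 × 0.05 = 1.5, 30 × 0.10 = 3 or 30 × 0.20 = 6. Their later observed values would still be summarised.

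**5. Could the early window matter?**

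Protocol 1.2.4 gives a median time to resolution of fever of 21.4 hours in the earlier Japanese pediatric study. If that time were exponential, the share of febrile infants already afebrile t hours after dosing would be 1 - 0.5^(t/21.4). This gives 3% at 1 h, 18% at 6 h, 32% at 12 h and 38% at 15 h. The distribution and the range of t are assumptions, and this trial does not require fever at entry. The figures show only that the window could be short and unimportant or long enough to matter.

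**The case against.** The strongest reply is that using diary temperature for safety is deliberate. Protocol 6.5 and SAP 4.2.1 both name it, and the schedule fixes its first reading as post-dose. Within that source no pre-dose baseline can exist, and one observer with one thermometer gives a consistent series. The documents do not state that reason, but it is sound. Replacing the diary baseline with a clinic value would mix site and caregiver readings, possibly from different devices. This part stands: a full swap of the diary baseline is a debatable trade-off, not a correction.

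Several stronger readings are tempting but unsupported:

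- *Clinic temperature will never be analysed.* SAP 4.2.1 allows safety parameters to be listed instead of summarised, so a listing remains open. What can be said is that no summary is specified.
- *Early changes vanish from the safety report.* Only the change column is affected. Observed diary values are summarised at each time point, and Protocol 5.3.5.5 requires clinically significant vital sign abnormalities to be reported as adverse events.
- *Infants without a Day 1 entry are lost.* They lose the change value only.
- *The SAP expects late device activation.* The rule beginning "In the case where the device was activated after Day 1, the actual day will be used as the assessment day" is a contingency in the efficacy section and implies no frequency.
- *Duration of Fever inherits the same baseline.* SAP 4.3.1 excludes infants who are afebrile at baseline but does not define that baseline, so this cannot be concluded.

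The reply does not explain the omission in SAP 4.2.1.4. Protocol 6.5 counts caregiver temperature among the vital signs. It does not say that the clinic reading drops out.

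**Conclusion.** The point holds as a gap in the specified summaries. Clinic tympanic temperature is a scheduled pre-dose vital sign within the primary safety endpoint, yet SAP 4.2.1.4 omits it. The only temperature change that is summarised starts after dosing.

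The consequence is limited. The study is single-arm and descriptive, so no test, error rate or decision rule changes. The data to close the gap are already scheduled for collection. The size of the omitted change cannot be stated, because the time to the first home reading and the frequency of missing Day 1 entries are not given. The temperatures and percentages above are illustrations. The conclusion rests on the texts and does not depend on them. It is a cheap improvement, worth making before the tables are produced.

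**What to change.** In SAP 4.2.1.4, add clinic tympanic temperature to the listed vital signs. Summarise it by scheduled visit, with change from the last pre-dose value as for the other four. This stays within one data source and gives change from before treatment at the four unconditional follow-up visits (Days 2, 4, 6 and 10), and at the conditional visits where measured. It does not depend on the diary, so it includes infants with no Day 1 entry.

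In SAP 4.2.1.5, keep the diary summary and label it 'change from first post-dose reading'. Optionally add a supportive change from the pre-dose clinic value to each diary reading, with a footnote on the possible observer and device difference. That would also give infants with no Day 1 entry a diary-based change.

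The cost is a few words in the SAP and one extra table, or one extra row per visit, from data already collected.

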#### **4.2.1.6 Exposure of Study Medication**

Study drug exposure will be summarized descriptively.

### **4.3 SECONDARY ENDPOINT ANALYSES**

#### **4.3.1 Efficacy Analyses**

The statistical analyses of efficacy endpoints will be descriptive. The ITTi set will be used for all efficacy analyses.

The data will be summarized using means, standard deviations, medians, and ranges for continuous variables and proportions for categorical variables, as appropriate.

Time-to-event endpoints and duration endpoints will be summarized using Kaplan-Meier plots and summaries of the median survival time.

Efficacy endpoints are based on the CARIFS questionnaire data which is recorded by the parent/caregiver using a handheld electronic device. This assessment data should be recorded for the following time periods:

**Table 4 CARIFS Questionnaire Data Recording Time Periods**

Period	Time a
Morning	05.00–10.59
Noon	11.00–14.59
Evening	15.00–18.59
Bedtime	19.00–23.59

a data should not be recorded between 00.00 and 04.59.

In the case where the device was activated after Day 1, the actual day will be used as the assessment day rather than the device-labelled day. In the case where assessments should be recorded twice daily (morning and evening) but are recorded for more than two time periods, only the morning and evening assessments will be presented in summaries over time. In the case where assessments should be recorded once daily but are recorded for more than one time period, a conservative approach will be taken to select the data points to be included in the summaries over time.

In the case where the recorded time of an assessment is outside the period time window for that assessment, the end time of the period should be imputed as the assessment time.

In the case where the assessment time falls into the period between 00.00 and 04.59 (due to technical error) the assessment date will be imputed to the date prior to recorded assessment date and the assessment time will be imputed to the end time of the period time window.

The possible scores for the 18 symptoms specified in the CARIFS questionnaire (see [Appendix 4](#)) are:

- 0 (“No Problem”)
- 1 (“Minor Problem”)
- 2 (“Moderate Problem”)
- 3 (“Major Problem”)
- 4 (“Don’t Know/Not Applicable”)

The imputation method used in the derivation of time to alleviation of influenza signs and symptoms is described below. No further imputation methods will be used.

In all time to event analyses, patients who withdraw prior to event of interest will be censored at the last observation timepoint.

If the number of patients in the ITTi set is small, then listings may be provided.

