### **Time to Alleviation of Influenza Signs and Symptoms**

Time to alleviation of influenza signs and symptoms (TTAS) in hours, will be summarized using descriptive statistics, as well as Kaplan-Meier plots. It is defined as the length of time taken from the start of treatment to the point at which all of the following criteria are met and remain so for at least 21.5 hours:

- A score of 0 (no problem) or 1 (minor problem) for cough and nasal symptoms (items 14 and 15 of the CARIFS questionnaire, see [Appendix 4](#)).
- A “yes” response to the following question on the CARIFS: “Since the last assessment has the subject been able to return to day care/school, or resume his or her normal daily activity in the same way as performed prior to developing the flu?”
- Return to afebrile state (tympanic temperature  $\leq 37.2^{\circ}\text{C}$ ).

If a score of 4 (“Don’t Know/Not Applicable”) occurs at any assessment during the study for items 14 or 15, the assessment will not be included in the calculation of the alleviation of symptoms because the assessment was unobservable.

Patients with symptom scores  $\leq 1$  for both items 14 and 15, as well as tympanic temperature  $\leq 37.2^{\circ}\text{C}$  and a “yes” response to the question “Since the last assessment has the subject been able to return to day care/school, or resume his or her normal daily activity in the same way as performed prior to developing the flu?” simultaneously at baseline will be excluded from the analysis.

Patients who do not experience alleviation of symptoms prior to completion or withdrawal from study will be censored at the last observation time point.

Baseline is defined as the first CARIFS assessment on Day 1 after the start of treatment. Patients who do not have a CARIFS assessment on Day 1 after the start of treatment will have their baseline CARIFS assessment set to missing.

The number of patients with completed CARIFS as well as the number with missing CARIFS per assessment will be presented for the ITT and ITTi sets. Additionally, the number and percentage of those with “Don’t Know/ Not Applicable” per question per assessment will be presented for the ITT and ITTi sets.

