### **Duration of Fever**

Duration of fever will be summarized using descriptive statistics, as well as Kaplan-Meier plots. It is defined as the time to return to afebrile state (tympanic temperature  $\leq 37.2^{\circ}\text{C}$ ) and remaining so for at least 21.5 hours.

Patients who do not return to afebrile state will be censored at the last observation time point.

Patients who are afebrile at baseline (tympanic temperature  $\leq 37.2^{\circ}\text{C}$ ) or whose body temperature is not collected will be excluded from the analysis.

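### The SAP has no TTAS rule for infants whose diary starts after Day 1; read as written, one already well at the first complete entry is counted as recovering exactly then

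*SAP*

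**What the plan says.** The relevant rules are all in SAP 4.3.1.

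- **Late devices.** The text under Table 4 provides for them: "In the case where the device was activated after Day 1, the actual day will be used as the assessment day". The rest of that sentence contrasts the actual day with the day label on the device. It is a dating rule and says nothing about inclusion.
- **Baseline.** The TTAS section takes the first post-dose Day 1 CARIFS as baseline. It adds: "Patients who do not have a CARIFS assessment on Day 1 after the start of treatment will have their baseline CARIFS assessment set to missing". SAP Appendix 2 (footnote g) places the first CARIFS after dosing, so no earlier entry can stand in.
- **Exclusion.** Infants who meet all three alleviation criteria "simultaneously at baseline will be excluded from the analysis". This is the only exclusion stated for TTAS.
- **Event time.** The definition of TTAS reads: "defined as the length of time taken from the start of treatment to the point at which all of the following criteria are met". Those criteria must then hold for at least 21.5 hours. The main analysis uses complete assessments only.
- **Censoring.** For all time-to-event analyses, "patients who withdraw prior to event of interest will be censored at the last observation timepoint". TTAS also censors infants who never reach alleviation at their last observation. Both rules are right-censoring, and further imputation is ruled out.
- **Sensitivity analyses.** Two are planned for TTAS. One concerns scores of 4 on items 14 and 15; the other drops the normal-activity question.

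**The concern.** When the diary begins late, the infant's state between dosing and the first entry is unobserved. If that entry shows an infant who is already well, recovery happened at some unknown earlier time. Scoring the entry as an exact event replaces the recovery time with its upper limit.

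TTAS is the key secondary efficacy endpoint. The study has one arm and about 30 infants, so the TTAS median is read on its own and no comparator shares the error. The rules also treat like infants differently: one who is well on Day 1 is excluded if the diary was running, but counts as an event days later if it was not.

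**Working it through.** The SAP states no figure on this point, so there is none to reproduce. The check has three steps.

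**1. Trace the rules for one infant.** Dosed at hour 0, truly well from hour 30, first complete entry at hour 72 with all criteria met and held.

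- No Day 1 CARIFS, so baseline is missing.
- The exclusion cannot be evaluated, so nothing removes the infant.
- The first complete entry is the earliest possible event time, so recorded TTAS = 72 h.
- Overstatement = 72 − 30 = 42 h.

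Had the infant still been ill at hour 72, the event would be dated at a later entry in the usual way, with no error from the late start. If an entry's clock time falls outside its diary period, the SAP moves it to the end of that period, so the recorded time is at or shortly after activation.

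**2. Size for one infant.** Take an exponential recovery time with median m = 44.6 h. That figure is from the Japanese paediatric study in Protocol 1.2.4, whose endpoint is similar but not identical (cough, nasal symptoms and fever only). With first entry at hour a:

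- P(already well) = 1 − 2^(−a/m)
- Mean overstatement if already well = [a − (m/ln 2) × P] / P, where m/ln 2 = 64.3 h

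| First entry a | P(already well) | Mean overstatement |
|---|---|---|
| 24 h | 0.31 | 13 h |
| 48 h | 0.53 | 27 h |
| 72 h | 0.67 | 43 h |
| 96 h | 0.78 | 60 h |

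For example, at 48 h: (48 − 64.3 × 0.526)/0.526 ≈ 27 h. A lognormal shape with log-SD 0.8 and the same median gives P = 0.22, 0.54, 0.73 and 0.83, and overstatements of about 8, 21, 36 and 54 h.

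**3. Size for the trial median.** Simulated trials of 30 infants (SAP 2.2), 40,000 per setting. Each infant starts late with the stated probability, at a time uniform over the stated window. Recorded time = max(true time, start time) for late starters, and the true time otherwise. Cells show the average rise in the sample median, in hours. The late-start rates, windows, shapes and the 66 h median are assumptions. The 66 h value allows for TTAS adding the normal-activity criterion, which can only lengthen an infant's time.

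| Start window | Late | Exp., 44.6 h | Lognormal, 44.6 h | Exp., 66 h | Lognormal, 66 h |
|---|---|---|---|---|---|
| 12–30 h | 10–20% | 0.1 or less | 0.0 | 0.0 | 0.0 |
| 24–72 h | 10% | 3.0 | 2.3 | 1.2 | 0.8 |
| 24–72 h | 20% | 5.6 | 4.5 | 2.3 | 1.4 |
| 48–96 h | 10% | 6.2 | 4.8 | 4.5 | 3.5 |
| 48–96 h | 20% | 12.2 | 9.8 | 8.2 | 6.5 |

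The shift was never negative in any simulated trial. Omitting every late starter instead changed the median by about 0.5 h or less on average. That holds because late starting was simulated as unrelated to recovery.

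**The case against.** **Retention is inferred.** A reader might conclude that the SAP has decided to keep these infants. It has not said so. Retention follows only from the absence of an exclusion, and the quoted sentence on late devices is about day labels. This stands, and it is why the point is worded as a missing rule with a consequence when read as written.

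**Long delays may be rare.** Visit 2 on Day 2 is mandatory (Protocol 3.1), site staff supply the device or its instructions (Protocol 4.5.6), and paper completion is allowed in exceptional circumstances (Protocol 7.1). A dormant device could be noticed about 24 hours after dosing, when the effect on the median is about 0. This also stands, though none of these provisions rules out longer gaps.

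**The shift is small against sampling error.** The simulated standard deviation of the median at 30 infants is 8 to 17 h, depending on shape and median, so an average shift of 1 to 3 h is well inside it. That is fair, but the shift has one direction and is avoidable.

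**The contrast with fever.** One might infer that duration of fever already solves the same problem, since it excludes infants "whose body temperature is not collected will be excluded from the analysis". That clause may mean never collected rather than not collected on Day 1, so it is not good evidence of an inconsistency. The argument does not need it.

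**An interval-censored estimate has its own flaw.** It would keep infants who might have been excluded had Day 1 been observed. With about 30 infants this is a reason to use it as a sensitivity analysis, not as the main estimator.

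**Counts are already planned.** The SAP will present the number with missing CARIFS at each assessment. That would reveal late starts but would not show how many were already well at first entry, and it corrects nothing.

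**Conclusion.** The point holds in a limited form. The TTAS section does not say how infants without a Day 1 post-dose CARIFS are handled. Applied literally, the rules give an exact event time to some infants for whom only an upper limit is known, and neither planned sensitivity analysis covers this.

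A reader might infer that TTAS as a whole measures when devices were switched on. The documents do not support that: only late starters already well at their first complete entry are affected. Nor do they support any single figure for the bias, because they give neither the number of late devices nor the delays. Under the stated assumptions the median moves by about 0 when all devices start by about 24 to 30 h, by roughly 1 to 3 h when 10% start at 24 to 72 h, and by more with later or more frequent late starts.

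The error lengthens TTAS, so it works against the drug. TTAS is descriptive, and the primary safety analysis is untouched. The point merits correction in the SAP but does not threaten the study's main conclusions.

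**What to change.** 1. In the TTAS section, state how infants without a Day 1 post-dose CARIFS enter the main analysis.
2. Add one sensitivity analysis of TTAS, in either form:
   - omit all infants with missing baseline. Dropping only those already well at first entry would selectively remove faster recoveries; or
   - keep them, and treat those already well at their first complete entry as interval-censored between dosing and that entry.
3. Report the number of infants with missing baseline, and how many of them already met all criteria at the first complete entry.

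The cost is a few sentences in the SAP, a little programming and one extra analysis; no new data are needed. Omission leaves slightly fewer infants and is valid only if late activation is unrelated to recovery. Interval-censoring avoids the loss but may retain infants whom the baseline rule would have removed. If no infant is affected, the results do not change.

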Appendix 1 **Schedule of Activities (cont.)**

- ^g The parent/caregiver will complete the CARIFS questionnaire twice (morning and evening) on Days 1 to 9 and then once daily on Days 10 to 15. *The first CARIFS assessment will occur post-dose.*
- ^h Perform if the investigator determines that influenza symptoms are persisting or at the investigator's discretion.
- ⁱ Record vital sign measurements if abnormal physical examination, adverse events recorded since last visit, or at investigator's discretion on Day 29.
- ^j At least two nasopharyngeal swabs (one for each nostril) will be taken at each visit.
- ^k *PK samples (all patients): See [Appendix 2](#) for collection timepoints for baloxavir marboxil and S-033447 concentration samples. Patients will be assigned to have either the Day 2 or the Day 4 sample. Only one sample from Days 6 to 10 is required and can be collected at either Visit 4 or Visit 5.*
- ^l *The palatability assessment should be completed by the study investigator (or delegate) who administers baloxavir marboxil to the patient.*

Appendix 2

Schedule of Pharmacokinetic Samples

Visit	Timepoint	Sample Type
Sparse PK Sampling ^a		
Visit 1 (Day 1)	One sample between 0.5 and 2 hours post-dose	Drug PK (plasma)
Visit 2 (Day 2) ^b	24 hours post-dose	Drug PK (plasma)
Visit 3 (Day 4) ^b	72 hours post-dose	Drug PK (plasma)
Visits 4 – 5 (Days 6 – 10)	Only one sample is to be collected during the follow-up period; this sample may be collected at follow-up Visit 4 or 5	Drug PK (plasma)

PK=pharmacokinetic.

^a Samples will be used for baloxavir marboxil and S-033447 determination.

^b Patients will be assigned to have either the Day 2 or the Day 4 sample.

Appendix 3
Canadian Acute Respiratory Illness and Flu Scale (CARIFS)
Questionnaire

Item	No Problem	Minor Problem	Moderate Problem	Major Problem	Don't Know/Not Applicable
1. Poor appetite					
2. Not sleeping well					
3. Irritable, cranky, fussy					
4. Feels unwell					
5. Low energy, tired					
6. Not playing well					
7. Crying more than usual					
8. Needing extra care					
9. Clinginess					
10. Headache					
11. Sore throat					
12. Muscle aches or pains					
13. Fever					

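### The SAP's rule for diary entries stamped 00:00–04:59 back-dates every entry by one day whatever its period label, so a Morning or Noon entry can be placed ahead of the previous evening's entry or before dosing

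*SAP*

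**What the plan says.** SAP 4.3.1, Table 4, divides the diary day into Morning (05:00–10:59), Noon (11:00–14:59), Evening (15:00–18:59) and Bedtime (19:00–23:59). Its footnote adds that "data should not be recorded between 00.00 and 04.59".

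Two imputation rules follow the table:

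- **General rule.** If an entry's time lies outside the window for its period, "the end time of the period should be imputed as the assessment time". No change of date is mentioned.
- **After-midnight rule.** If the time lies between 00:00 and 04:59, which the SAP puts down to a technical fault, "the assessment date will be imputed to the date prior to recorded assessment date". The clock reading is replaced as well: "the assessment time will be imputed to the end time of the period time window". No period label is excepted, and nothing checks the result against dosing or the order of entries.

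The labels in use come from the schedule. Protocol Appendix 1 (repeated in SAP Appendix 2) states: "The parent/caregiver will complete the CARIFS questionnaire twice (morning and evening) on Days 1 to 9". It also states: "The first CARIFS assessment will occur post-dose". Temperature is scheduled in all four periods on Days 1 to 3 and in the morning and evening on Days 4 to 9.

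SAP 4.3.1 measures TTAS as "the length of time taken from the start of treatment to the point at which all of the following criteria are met", and the criteria must "remain so for at least 21.5 hours". The same hold applies to duration of fever, duration of symptoms and return to normal activity. Baseline is the first post-dose Day 1 assessment, and patients already meeting all TTAS criteria at baseline are excluded from that analysis.

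**The concern.** Moving an after-midnight entry to the previous date makes sense when it is a late entry for the evening or bedtime just past. It does not make sense for an early entry for the morning to come. Morning is one of only two scheduled CARIFS labels on Days 1 to 9, so this is not an unused category.

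Endpoints with a 21.5-hour hold depend on the order of entries as well as their times. One record moved past its neighbour can hide a relapse, interrupt a true run of alleviation, or change the baseline and so decide whether a patient is analysed. The two planned TTAS sensitivity analyses vary the handling of score 4 and the normal-activity criterion; neither varies timing. With about 30 patients planned, one or two such records could be visible in a Kaplan-Meier summary.

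**Working it through.** The plan gives no figure to reproduce; the check is clock arithmetic.

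**Inputs.** Period end times from SAP Table 4; the two rules in SAP 4.3.1; the 21.5-hour hold. Dosing and entry times in the examples are assumed.

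**Size of the shift, using the entry's own label**

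After-midnight rule: shift = period end − 24h00 − stamp, for stamps from 00:00 to 04:59.

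| Label | Period end | Stamp 00:00 | Stamp 04:59 |
|---|---|---|---|
| Morning | 10:59 | −13h01 | −18h00 |
| Noon | 14:59 | −9h01 | −14h00 |
| Evening | 18:59 | −5h01 | −10h00 |
| Bedtime | 23:59 | −0h01 | −5h00 |

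The Evening and Bedtime shifts are what a late entry needs. The Morning and Noon shifts are errors if the entry belongs to the recorded date. Both land at or before 14:59 on the previous day, so before that day's evening window opens at 15:00.

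**Conflict between the rules**

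For a Morning entry at 04:45 on Day 3:

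- General rule: Day 3 10:59, which is 6h14 later.
- After-midnight rule: Day 2 10:59, which is 17h46 earlier.
- Difference: 6h14 + 17h46 = 24h00.

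**Position relative to dosing**

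A Morning entry stamped Day 2 04:30 becomes Day 1 10:59.

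- Dosing Day 1 14:00: the entry moves from +14h30 to −3h01, ahead of both dosing and a Day 1 evening entry at 18:00 (+4h00). Any Day 1 dosing after 10:59 puts it before treatment.
- Dosing Day 1 09:00: it lands at +1h59. If no real post-dose entry was made earlier that day, it becomes the baseline; if it meets all the TTAS criteria, the patient drops out of the TTAS analysis.

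**Effect on the hold** (all TTAS components assumed to move together)

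- *False hold.* Day 2 18:00 alleviated; Day 3 04:45 Morning not alleviated; Day 3 18:00 alleviated. The relapse moves to Day 2 10:59. Day 2 18:00 to Day 3 18:00 is then an unbroken 24h00, which meets 21.5 hours. Onset becomes Day 2 18:00, when it could not have been before Day 3 18:00.
- *Broken hold.* Day 2 18:00 not alleviated; alleviated from Day 3 04:45 Morning onward, next entry Day 3 18:00. The first alleviated entry moves to Day 2 10:59 and is followed by the non-alleviated evening. Onset becomes Day 3 18:00, 13h15 after 04:45.
- *Already alleviated.* If the Day 2 evening entry was alleviated, an alleviated Day 3 04:45 entry moved to Day 2 10:59 brings onset forward by 4h01 (evening at 15:00) to 8h00 (evening at 18:59).

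The moved record may also duplicate the previous day's real Morning entry. The SAP's rule for multiple values in a window belongs to Table 2, which excludes diary data.

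**The case against.** The strongest reply is that the SAP regards these stamps as faulty: it says none should exist and attributes them to technical error. If the clock is wrong, the recorded hour is no guide to the truth. This limits how often the rule should bite, but the trigger is the clock time alone, with no evidence of a fault required, and a faulty stamp is no reason to move a Morning entry to the previous day.

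Second, the 13h01 to 18h00 figure is conditional. If the period window meant the Bedtime period just ended, the shift would be 0h01 to 5h00. If the entry was a late one for the previous morning, back-dating would be right. The documents also do not confirm that the device lets a Morning label be attached at these hours. These points stand as conditions. However, the general rule refers to the window belonging to that assessment, which favours the own-label reading, and Bedtime is not a scheduled CARIFS period.

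Third, the after-midnight rule is the more specific one and would probably be taken to override the general rule. That is likely, but it is the reading that produces the misordering.

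Fourth, a reader might infer that TTAS itself is wrong by up to 18 hours. The documents do not support equating the two: the error in onset depends on the neighbouring entries, as the examples show. Nor does the 44.6-hour median quoted in Protocol 1.2.4 give a scale. It comes from children aged 6 months to under 12 years, on an endpoint without the normal-activity criterion, and it is a group median rather than one patient's timing.

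Fifth, a reader might infer that the general period-end convention should give way to raw time stamps. That is a matter of preference. The convention moves a Morning entry made at 14:00 back by 3h01 and an Evening entry made at 14:00 forward by 4h59; it is a nominal-time choice, not an error.

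**Conclusion.** The point holds as a defect in a stated rule. Applied to a Morning or Noon label, the after-midnight rule can give a wrong order of assessments, and the SAP does not say how it ranks against the general rule, which gives a result 24 hours away. The misplacement is 13h01 to 18h00 for Morning and 9h01 to 14h00 for Noon.

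This rests on three assumptions: the period window is that of the entry's own label; the entry belongs to the recorded date; and the rules cover diary temperature as well as CARIFS. The third is an inference: Table 4 names only CARIFS, but its Noon and Bedtime periods are scheduled only for temperature. Placement before dosing further needs a Day 2 Morning entry with dosing after 10:59 on Day 1.

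The documents do not say how many such entries to expect. The endpoints are secondary and descriptive and no hypothesis is tested, so no error rate or sample size is affected and the effect on the summaries may be small. It is worth correcting because a single record can change a patient's TTAS value or inclusion.

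**What to change.** Amend SAP 4.3.1 as follows:

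- Apply the previous-date rule only to entries labelled Evening or Bedtime, and say that the window used is that of the entry's own label.
- For entries labelled Morning or Noon and stamped 00:00–04:59, keep the recorded date unless there is documented evidence that the entry belongs to the previous day. With the date kept, the existing period-end convention puts a Morning entry at 10:59 that day, 6h00 to 10h59 after its stamp, and it cannot pass the previous evening's entry.
- State that this rule takes precedence over the general out-of-window rule.
- State that no imputed time may precede dosing or the preceding diary entry, and what is done with a record that fails this check.

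The general period-end convention can stay. The cost is a few sentences in the SAP and minor programming, to be completed before database lock.
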